9. RESEARCH METHODS

9.1 Study design

We will take advantage of the unique nationwide register-data available to us, and construct country-specific cohorts with individual-level information on dates of vaccination and dates of effectiveness endpoints together with relevant covariate information. All Nordic residents are assigned a unique personal identifier at birth or immigration, enabling linkage between register data. Nordic countries have universal and tax-financed healthcare systems and reporting to national registers is mandatory, providing near-complete follow-up of all residents over time.

The study period will start on 1st October 2024 in the three countries. This study start date corresponds to the start of the seasonal influenza vaccination program in the three countries. The study period will end on the last date of data availability at time of analyses during spring 2025.

The study design will build on our previous work with Covid-19 vaccination effectiveness in the Nordic countries (19,20). We will utilize a cohort design in a target trial emulation (TTE) framework to estimate both relative and absolute effects. The evaluations in 65+-yr-olds and risk groups 18-64-yr-olds will be designed as two separate target trial emulations. Key components of the specification and emulation of the pragmatic target trials of the effectiveness of brand-specific seasonal IVE using Nordic nationwide register data are included below in Table 1.

Table 1. Target trial emulation framework

Protocol	Target Trial Specification	Target Trial Emulation
Eligibility criteria	
 • Individuals 65+-years-of-age (trial 1) • Individuals in risk groups 18-64-yr-of-age (trial 2) • Have a permanent residency in Denmark, Finland, or Sweden at start of study period 	Same as for the target trials.
Treatment strategies	Vaccination with any of the following influenza vaccines InfluvacTetra, VaxigripTetra, FludTetra, FluarixTetra or Efluelda Tetra, October 1, 2024 to January 31, 2025 vs vaccination with placebo in the same period.	Same as for the target trials except vaccination with placebo is replaced by no vaccination with any of the vaccines under study.

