	Finland	The Finnish Population Information System. Recorded birth year. Age defined as 2024 minus birth year.	
	Sweden	The Total Population Register. Recorded birth year. Age defined as 2024 minus birth year.	
Sex	Denmark	The Civil Registration System. Defined as registered sex.	Binary: male, female
	Finland	The Finnish Population Information System. Defined as registered sex.	
	Sweden	The Total Population Register. Defined as registered sex.	
Region of residency	Denmark	The Civil Registration System. Defined by last known address at the start of the study period.	Categorical: Denmark, 5 levels; Finland, 5 levels; Sweden, 9 levels
	Finland	The Finnish Population Information System. Defined by last known municipality of residence.	

Variable	Country	Data source and details	Values/codes
	Sweden	The Total Population Register . Defined by last known address at the start of the study period.	
Comorbidity 1: Chronic pulmonary disease	Denmark	The National Patient Register . Defined as primary or secondary diagnoses registered prior to the start of the study period (look-back 7 years).	Binary: yes/no (ICD-10 codes: J40-J47, J60-J67, J684, J701, J703, J841, J920, J961, J982, J983)
	Finland	Care register for Health Care . Defined as primary or secondary diagnoses registered prior to the start of the study period (look-back 7 years).	Binary: yes/no (ICD-10 codes: J41-J44, J47)
	Sweden	National Patient Register . Defined as any recorded ICD-10 diagnosis during inpatient or outpatient contact and before first Covid-19 vaccination (look-back 7 years).	Binary: yes/no (ICD-10 codes: E84, J41-J47, J84, J98)
Comorbidity 2: Cardiovascular conditions	Denmark	The National Patient Register . Defined as primary or secondary diagnoses registered prior to the start of the study period (look-back 7 years).	Binary: yes/no (ICD-10 codes: I110, I20-I23, I420, I426-I429, I48, I500-I503, I508, I509, I60-I65)
	Finland	Care register for Health Care, Register of Primary Health Care Visits, Special Reimbursement Register and Prescription Centre database . Defined as primary or secondary diagnoses prior to the start of the study period (look-back 7 years).	Binary: yes/no (ICD-10 codes: I11-I13, I15, I20-I25, I60-I65)

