	Sweden	National Patient Register . Defined as any recorded ICD-10 diagnosis during inpatient or outpatient contact prior to the start of the study period (look-back 7 years).	Binary: yes/no (ICD-10 codes: I05-I09, I110, I20-I28, I34-I37, I39, I42, I43, I46, I48-I50, I60-I65)
Comorbidity 3: Diabetes	Denmark	The National Patient Register . Defined as primary or secondary diagnoses registered prior to the start of the study period (look-back 7 years).	Binary: yes/no (ICD-10 codes: E10-E11)
	Finland	Care register for Health Care, Register of Primary Health Care Visits, Special Reimbursement Register and Prescription Centre database . Defined as primary or secondary diagnoses prior to the start of the study period or drug prescriptions (look-back 7 years).	Binary: yes/no (ICD-10 codes: E10, E11, E13-E14; ICPC-2 codes: T89, T90; ATC codes: A10A, A10B)
	Sweden	National Patient Register . Defined as any recorded ICD-10 diagnosis during inpatient or outpatient contact prior to the start of the study period (look-back 7 years). Swedish Prescribed Drug Register . Antidiabetic drugs use defined as ≥ 2 filled prescriptions during 2020.	Binary: yes/no (ICD-10 codes: E10-E14; ATC code: A10)
Comorbidity 4: Autoimmunity-related conditions ^a	Denmark	The National Patient Register . Defined as primary or secondary diagnoses registered prior to the start of the study period (look-back 7 years).	Binary: yes/no (ICD-10 codes: D510, D590, D591, D690, D693, D86, E050, E063, E271, E272, G122G, G35, G610, G700, I00, I01, K50, K51, K743, K900, L12, L40, L52, L80, L93, M05, M06, M08,

Variable	Country	Data source and details	Values/codes
			M300, M313, M315, M316, M32, M33, M34, M35, M45)
	Finland	Care register for Health Care, Special Reimbursement Register and Prescription Centre database. Defined as primary or secondary diagnoses prior to the start of the follow-up or drug prescriptions (look-back 7 years).	Binary: yes/no (ICD-10 codes: D7081, D7089, D80–D84, E250, E271, E272, E274, E310, E896, D86, K50, K51, L40, M02, M05–M07, M139, M45, M460, M461, M469, M941; ATC-codes: H02AB02, H02AB04, H02AB06, H02AB07, L01BA01, L01XC02, L04AA06, L04AA10, L04AA13, L04AA18, L04AA24, L04AA26, L04AA29, L04AA33, L04AA37, L04AB, L04AC, L04AD01, L04AD02, L04AX01, L04AX03)

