9.7 Data analysis

Procedures

We will use a matched cohort design to evaluate the effectiveness of seasonal influenza vaccine in comparison with not receiving a seasonal influenza vaccine. Individuals who have received the vaccine will be matched on the day of vaccination with individuals who have not yet received the vaccine. Individuals will be matched on age (5-year bins), sex, region of residence, and selected comorbidities. The day the seasonal vaccine dose was administered within each matched pair will serve as the index date for both individuals. If individuals who were included as a matched non-vaccinated individual

(i.e., a reference individual) receive a vaccine later than the assigned index date, the pair will be right-censored on the day the non-vaccinated individual is vaccinated. In these cases, the non-vaccinated individuals will be allowed to potentially re-enter as vaccine recipients in a new matched pair on that given date.

Statistical analysis

We will follow individuals from day 14 after the index date (to ensure full immunisation) up until the day of an outcome event, death, emigration, or end of the study, whichever occurs first. Additionally, we will censor individuals with a positive PCR test for influenza in our follow-up period 14 and 30 days after the test (as a positive test will be part of the outcome definitions) for the influenza hospitalisation and death outcome analyses, respectively. We will right-censor matched pairs when the reference unvaccinated individual receives a vaccine during follow-up. Cumulative incidences will be estimated by the Aalen-Johansen estimator, and from these we will calculate the comparative VE as $1 - \text{risk ratio}$ at the start of week 18 (depending on data availability) since index date. The corresponding 95% CI will be calculated using the delta method. Country-specific estimates will be combined by random-effects meta-analyses implemented using the *mixmeta* package in R.

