9.8 Supplementary analyses and quality control

Confounding-by-indication and healthy vaccinee bias are critical methodological concerns in studies of influenza VE. (46). Confounding by indication would result in an underestimate of true effectiveness if individuals with comorbidities that increase the risk of the study outcome are more likely to get vaccinated. Healthy vaccinee bias occurs when healthy individuals are more likely to get vaccinated while the most frail and sick elderly with the highest risk of the study outcome are not vaccinated, especially at the end of life. In Table 8 below, we present the key possible confounders in studies of effectiveness and how they are likely to be associated with study exposures and outcomes.

Table 8. List of possible confounders in IVE studies

Possible Confounder	Influenza vaccination propensity	Influenza hospitalisation risk	All-Cause Mortality risk	Bias Direction for VE against	Bias direction for VE against

				influenza hospitalisation	all-cause mortality
Comorbidity	↑	↑	↑	Underestimate	Underestimate
High frailty	↓	↑	↑	Overestimate	Overestimate
Healthcare seeking	↑	↑	↓	Underestimate	Overestimate
Healthcare access	↑	↑	↓	Underestimate	Overestimate

The current state-of-the-art in observational vaccination effectiveness estimation is comprised mainly of two study approaches, the test-negative design and TTE. Both approaches seek to mitigate the impact of bias and confounding. Guilin and colleagues (47) evaluated the performance of the two approaches in the evaluation of Covid-19 VE estimation. In data with rich covariate information, they observed similar VE estimates from the two methods. In data with only a few covariates, the test-negative design tended to overestimate the VE, while the target trial emulation underestimated the VE.

To evaluate the potential for biases by healthcare-seeking behaviour or healthcare access, the TTE will be supplemented by a TND study. The TND study is only feasible in Denmark due to lack of test-negative results in Finland and Sweden. Moreover, supplementary analysis comprising of PERR, RDA, and Negative Control Outcomes Analyses will be conducted to allow for comparison and contextualisation of results. Moreover, to strengthen the robustness of findings, triangulation—integrating evidence from multiple analyses with different methodologies—can provide valuable insights into potential biases and enhance the interpretation of results.

Test-Negative Case Control design

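### Matching comorbidities are mostly read at 1 October 2024 instead of the pair's index date, and current inpatients may serve as unvaccinated controls, so VE may be biased, most plausibly upward for mortality

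*Protocol*

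**What the plan says.** Section 9.7 forms pairs day by day: "Individuals who have received the vaccine will be matched on the day of vaccination with individuals who have not yet received the vaccine". Table 1 (Section 9.1) gives the vaccination window as "October 1, 2024 to January 31, 2025 vs vaccination with placebo in the same period".

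The comorbidity matching factor is a count (0, 1, 2, or 3 and more) of six chronic conditions, defined by country in Table 6 (Section 9.3). The Danish rows read "Defined as primary or secondary diagnoses registered prior to the start of the study period (look-back 7 years". On that date Section 9.1 says: "The study period will start on 1st October 2024 in the three countries".

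Three items in Table 6 depart from this cut-off:
- Finland, autoimmunity-related conditions: "Defined as primary or secondary diagnoses prior to the start of the follow-up or drug prescriptions (look-back 7 years"
- Sweden, chronic pulmonary disease: "Defined as any recorded ICD-10 diagnosis during inpatient or outpatient contact and before first Covid-19 vaccination (look-back 7 years"
- Sweden, the drug component of diabetes: "Antidiabetic drugs use defined as ≥ 2 filled prescriptions during 2020"

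Eligibility (Table 1 and Section 9.2) consists of age or risk group and residency at study start. Neither eligibility nor matching mentions current or recent admission.

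**The concern.** In a target trial emulation, baseline status should be known as of assignment. Here assignment is the index date, while the health status used for matching is read at a fixed earlier date. The gap grows as the season goes on.

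Two separate problems follow:
- **The date of the chronic-condition count.** Someone diagnosed with cancer or heart failure in November still counts as free of it when matched in December or January.
- **No rule on admission at index.** A person lying in hospital on the index date counts as not yet vaccinated and can be drawn as the control for someone well enough to attend for a vaccine.

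Section 9.8 itself describes the second mechanism, noting that healthy people tend to be vaccinated "while the most frail and sick elderly with the highest risk of the study outcome are not vaccinated, especially at the end of life". The vaccination sites listed in Section 9.3 are general practices, regional centres and workplaces, not wards. Because a pair is censored when its control is vaccinated, controls too ill to be vaccinated would also tend to stay under follow-up longer. What is at stake is mainly VE against death with influenza (primary) and all-cause mortality (secondary).

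**Working it through.** The plan gives no figure of its own to reproduce here.

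**1. How uniform is the cut-off?** Table 6 has 6 conditions × 3 countries = 18 rows. For diagnoses, 16 close at study start (Denmark 6, Finland 5, Sweden 5). The other two are Finnish autoimmunity and Swedish pulmonary disease. The Swedish diabetes row closes its diagnoses at study start but takes its drug component from 2020.

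**2. Lag from 1 October 2024**

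| Index date | Days to index | Days to start of follow-up (+14) |
|---|---|---|
| 1 October 2024 | 0 | 14 |
| 20 December 2024 | 80 | 94 |
| 31 January 2025 | 122 | 136 |

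Section 9.5 gives Danish coverage at 65 and over as 75.6% by 20 December. Even if everyone else were vaccinated later, at least 75.6% of those vaccinees would have a lag of 80 days or less. The 122 days is the extreme.

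**3. Possible size.** Let p0 and p1 be the shares of controls and vaccinees who became seriously ill after 1 October or are admitted at index, and let R be their outcome risk ratio against others. Then

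observed RR = true RR × [1 + p1(R − 1)] / [1 + p0(R − 1)].

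The documents give none of these inputs. The assumed ranges are p0 from 0.5% to 3%, R from 2 to 10, and p1 from 0 to 1.5 times p0. Example with true VE 40%, p0 = 1%, R = 5, p1 = 0: 0.60 × 1/1.04 = 0.577, so observed VE is 42.3%.

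Observed VE (%) when true VE is 40%:

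| p1 / p0 | p0 0.5%, R 2 | p0 1%, R 5 | p0 2%, R 5 | p0 3%, R 10 |
|---|---|---|---|---|
| 0 | 40.3 | 42.3 | 44.4 | 52.8 |
| 0.5 | 40.1 | 41.2 | 42.2 | 46.4 |
| 1 | 40.0 | 40.0 | 40.0 | 40.0 |
| 1.5 | 39.9 | 38.8 | 37.8 | 33.6 |

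With a true VE of 0 and p1 = 0, the same four columns give an apparent VE of 0.5%, 3.8%, 7.4% and 21.3%.

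The sign depends on whether new illness lowers or raises uptake. When it is balanced at index (p1 = p0) the bias disappears for any p0 and R. Re-dating the six-condition count would not achieve that balance alone, because current admission and most acute illness are not part of the count.

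**4. Do the planned safeguards cover it?**
- The Day 0 to 14 analysis, PERR and RDA address influenza hospitalisation only.
- The Danish test-negative study addresses infection.
- The negative control outcomes (back pain, clavicle fracture, diverticulitis) are weak markers of acute severe illness.
- Starting follow-up on day 14 removes the first two weeks after index, not the later excess.

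These may reveal part of the bias. None corrects the main estimate, and none of those tied to an influenza outcome looks at mortality.

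**The case against.** The strongest reply concerns direction. A reader might infer that this gap inflates VE across the board. The protocol does not support that. Table 8 says comorbidity raises vaccination propensity and makes VE an underestimate for both hospitalisation and mortality. A missed new diagnosis of chronic disease may therefore push VE down, as in the last row of the first VE table. Only acute or terminal illness points upward. For hospitalisation outcomes, a person still in hospital cannot have a new admission, which works the other way.

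A reader might also infer that every comorbidity is frozen at 1 October, or that re-dating is trivial everywhere. Neither is right. Three items use other dates. Table 7 lists the Finnish reimbursement and prescription databases as available 1995 to 2023, updated every 6 months, so on that listing they end at least nine months before 1 October 2024. They feed the Finnish cardiovascular, diabetes, autoimmunity and (reimbursement only) cancer rows and cannot be brought up to the index date. The Finnish and Swedish hospital registers record discharge diagnoses, so someone still admitted at index may have no dated diagnosis yet.

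The protocol also names healthy vaccinee bias, lists confounding as a limitation, starts follow-up at day 14 and plans several supplementary analyses. All of this stands, and it limits the claim about sign, size and ease of repair. It does not explain why baseline health is read before assignment, nor why inpatients are left in the control pool.

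**Conclusion.** The point holds as a misalignment between baseline health and assignment. For 16 of 18 Table 6 rows diagnoses close at 1 October 2024, index dates run up to 122 days later, three items use other anchors, and nothing excludes a current inpatient as a control. VE may be biased. Upward bias is most plausible for all-cause mortality and death with influenza, since the protocol itself says the sickest go unvaccinated. The direction is uncertain for hospitalisation outcomes and for newly diagnosed chronic disease.

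The size cannot be found from the documents. Under the assumed ranges it is a few VE points in mid-range scenarios, and more than 10 points only in extreme ones. Those figures illustrate sensitivity and do not estimate the bias. The change should be made because it improves alignment whichever way the bias runs.

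**What to change.** 1. In Table 6, define each comorbidity from diagnoses recorded before the pair's index date, with the same 7-year look-back, wherever the register holds dated contacts up to that date.
2. For the Finnish reimbursement and prescription sources, use the latest available data and state the date at which they end.
3. Bring the Finnish autoimmunity, Swedish pulmonary and Swedish antidiabetic items to the same anchor.
4. Add to eligibility, for both pair members, that the person is not a hospital inpatient on the index date. Step 1 does not do this by itself, so both changes are needed.

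Cost: for the hospital registers this means a changed date rule in the common data model and one filter on admission and discharge dates. It brings time-updated matching strata, hence more computing, and some lost pairs. A residual lag remains in discharge-based diagnoses and in the Finnish prescription data, and should be listed in Section 9.9.

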Finland (23)	
 - Pregnant women - Individuals aged 65 years or more - Children aged under 7 years - Individuals at risk because of illness or treatment 
 ○ Chronic heart disease ○ Chronic lung disease ○ Chronic metabolic disease ○ Chronic liver disease ○ Chronic kidney disease ○ Immunocompromising conditions due to disease or treatment ○ Down syndrome ○ A neurological disease affecting breathing ○ Psychotic disease ○ Obesity (body mass index > 40) ○ Other condition causing susceptibility for severe influenza - Those close to a person susceptible to serious influenza - Social welfare, healthcare and medical care personnel - Men starting their military service and women starting their voluntary military service

¹For example, persons with immunoglobulin deficiencies, organ or stem cell transplantation, cancer undergoing chemotherapy, or persons undergoing other immunosuppressive treatment.

² For example, persons with severe rheumatological disease, severe neurological disease, or short bowel syndrome.

³ For example, persons with severe mental illness, Down syndrome, or severe substance abuse.

⁴ Pregnant women with other risk factors for a severe course of influenza are recommended to receive the influenza vaccine starting from the first trimester.

Table 3: Overview of vaccine brands used in the national programmes in the Nordic countries in season 2024/2025

Country	Vaccine Brand	Vaccine Type	Target population
Denmark	InfluvacTetra®	QIV, surface antigen	Risk groups above 6 months Individuals 65-69 years
	Vaxigrip Tetra®	QIV, split virion	Risk groups above 6 months Individuals 65-69 years
	Efluelda Tetra®	QIV, adjuvanted (high-dose)	Clinical trial, 65+
	Fluad Tetra®	QIV, adjuvanted	Elderly 70+
	Flucelvax Tetra®	QIV, surface antigen, cell-based	Individuals with serious allergy to egg, neomycin or gentamycin
Finland	Vaxigrip Tetra®	QIV, split virion	All target groups (incl. 2-6-year-olds)
	Fluenz®	Attenuated live virus, nose spray	Children 2-6 years
	Fluad Tetra®	QIV, adjuvanted	Elderly ≥85y Severely immunocompromised ≥50y
	Efluelda Tetra®	QIV, adjuvanted (high-dose)	Outside national vaccination program
Sweden	Vaxigrip Tetra®	QIV, split virion	All target groups (risk groups above 6 months and all above 65)
	InfluvacTetra®	QIV, surface antigen	All target groups (risk groups above 6 months and all above 65)

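### Two Swedish comorbidity windows in Table 6 do not end at the study start: pulmonary disease stops at the first Covid-19 vaccination, and antidiabetic use is read in 2020 only

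*Protocol*

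**What the plan says.** Section 9.3 matches exactly on age, sex, region and the number of six selected comorbidities, grouped as 0, 1, 2 or at least 3. Table 6 defines each comorbidity by country.

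- Chronic pulmonary disease, Sweden: any inpatient or outpatient diagnosis "before first Covid-19 vaccination (look-back 7 years").
- Diabetes, Sweden, has two routes. The diagnosis route uses the window common to the other Swedish rows. The drug route reads "Antidiabetic drugs use defined as ≥ 2 filled prescriptions during 2020".
- Cardiovascular, autoimmunity-related, cancer and renal conditions, Sweden, and the diabetes diagnosis route: "Defined as any recorded ICD-10 diagnosis during inpatient or outpatient contact prior to the start of the study period (look-back 7 years").

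The footnote to Table 6 explains why diagnosis codes differ between countries: expert input and national registration practice. It does not mention time windows. Section 9.1 says that the design builds on the group's Covid-19 vaccine work.

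**The concern.** A covariate used for matching at an index date in the 2024-2025 season should describe health shortly before that season, by one rule for everyone. The Swedish pulmonary rule fails on three counts. It drops the most recent diagnoses. It has no end date for a person who never had a Covid-19 vaccine. And its end date is set by earlier vaccination behaviour, which plausibly goes with influenza vaccination.

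The comorbidity count is the only measure of health status in the primary analysis, and Section 9.7 adds no regression adjustment to the Aalen-Johansen risk ratio after matching. If the count is measured differently in the two arms, pairs that look balanced may not be. The matching diagnostics in Section 9.8 check the recorded variable, so they would not show this.

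**Working it through.** The plan gives no figure to reproduce. The check sets the rows of Table 6 side by side and then does date arithmetic.

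**1. Which cells differ.** Table 6 has 6 comorbidities × 3 countries = 18 cells. Section 9.1 fixes the anchor: "The study period will start on 1st October 2024 in the three countries". The Danish and Finnish pulmonary rows use it: "Defined as primary or secondary diagnoses registered prior to the start of the study period (look-back 7 years"). So do the five other Swedish diagnosis windows. Among the Swedish definitions, two depart from it: pulmonary disease and the drug route for diabetes.

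**2. Pulmonary window.** The protocol gives no date of first Covid-19 vaccination. I assume a date between 27 December 2020 and 31 December 2021.

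- Gap from first dose to 1 October 2024: 3.76 years for the earliest date, 2.75 years for the latest.
- Overlap with the seven-year window used elsewhere (1 October 2017 to 1 October 2024): 7 − 3.76 = 3.24 years, up to 7 − 2.75 = 4.25 years.
- Seven years before the first dose reaches back to late December 2013 or late December 2014. Table 7 gives the availability of the Swedish patient register as 2017 onwards. Counting from 1 January 2017, the usable window is about 4.0 to 5.0 years. A window ending at the study start would lie wholly inside the available data.

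**3. People with no Covid-19 vaccination.** The text gives no end date, while the missing-data paragraph of Section 9.4 says every covariate is either present or not. Two codings are possible. Suppose, as is plausible but not shown in the protocol, that these people are commoner among the influenza-unvaccinated:

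- If they are read up to the study start, controls are better ascertained. At the same recorded count, vaccinated members then carry more hidden disease, and VE is biased downward.
- If they are coded as free of pulmonary disease, the hidden disease sits mainly in controls, and VE is biased upward.

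The direction therefore depends on a coding choice that the protocol does not make.

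**4. Drug route for diabetes.** From 31 December 2020 to 1 October 2024 is 1,370 days, and 1,370 / 365.25 = 3.75 years. Treatment started in that time does not count by this route. A person with a hospital inpatient or outpatient diabetes diagnosis up to the study start is still captured. The loss is limited to people identifiable only from later prescriptions.

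**5. Reach.** From Section 9.5, the Swedish share of the stated 65+ population is 280,000 / (1,211,000 + 1,315,000 + 280,000) = 280,000 / 2,806,000 = 10.0%. Random-effects weights are not population shares, so this is only a guide to Sweden's weight in the pooled estimates.

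**The case against.** The best defence is that only two definitions are affected, in the smallest of the three countries. One of the two has a diagnosis route that still runs to the study start. The plan also has checks aimed at residual confounding: negative control outcomes in the main design and the prior event rate ratio analysis (Section 9.8). All of this stands and limits the consequence. It does not make the windows right. The supplementary checks may signal confounding but do not repair a matching variable, and the test-negative analysis is Danish only.

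Four stronger readings are tempting, and the protocol does not support them.

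- *Both windows depend on vaccination behaviour.* Only the pulmonary one does. The year 2020 is the same for everyone.
- *A stated loss of VE can be attached to this.* That needs the prevalence of hidden disease in each arm and its risk ratio. The protocol gives neither, and the direction is open as well.
- *The Finnish code lists share the fault.* The Finnish cardiovascular list, "I11-I13, I15, I20-I25, I60-I65", omits I42, I48 and I50, and the Finnish cancer list omits C81-C96. A reader might set this against Table 2, which names "Immunocompromising conditions due to disease or treatment" as a Finnish target group. But the Table 6 footnote gives a reason for country-specific codes. The same codes apply to both members of a Finnish pair, and Finnish Comorbidity 4 captures part of the immunocompromised group through D80-D84 and drug codes.
- *The windows were copied from a Covid-19 protocol.* The wording and Section 9.1 make this likely, but it remains an inference and the point does not need it.

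**Conclusion.** The point holds for the two Swedish windows and no further. As written, the pulmonary rule discards about 2.75 to 3.76 years of recent diagnoses (on the assumed first-dose dates), is undefined for people never vaccinated against Covid-19, and ties ascertainment to past vaccination behaviour. The 2020 prescription rule is out of date by 3.75 years but is the lesser fault. No reason is given for either. Both can leave residual confounding in the Swedish estimates, which are reported by country as well as pooled. The effect on the meta-analysis is limited by Sweden's size. That ascertainment differs between arms rests on the assumption that Covid-19 and influenza vaccination go together.

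**What to change.** In Table 6, give Swedish chronic pulmonary disease the same window as the other Swedish diagnosis rows: diagnoses in the seven years up to the start of the study period. Anchor the antidiabetic prescription rule to the same date instead of calendar year 2020. At least two fills in the preceding 12 months would do, as would the seven-year look-back that Finland uses for prescriptions. Either is acceptable if stated before matching is run.

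The cost is two table cells and the matching parameters in the Swedish data preparation. Table 7 lists the patient register from 2017 to the present with a lag of 2 to 4 weeks, so the pulmonary change needs no new data. For the Prescribed Drug Register, Table 7 gives availability only as 2017, with monthly updates and a two-week lag. The sponsor should confirm that the extract runs to September 2024. Table 7 describes the Swedish vaccination sources as holding influenza vaccinations, and the change also removes any need for Covid-19 vaccination dates.
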